## **5.2 Exclusion Criteria**

Patients meeting any of the following exclusion criteria are not to be enrolled in the study:

### **5.2.1 Phase 1b and Phase 2**

1. Prior anticancer therapy or other investigational therapy within 2 weeks before administration of the first dose of MLN0128 (except for exemestane or fulvestrant, which should be continued). Treatment with everolimus must be discontinued 2 weeks before administration of the first dose of MLN0128.
2. Chronic concomitant therapy with bisphosphonates or denosumab for the prevention of bone metastases. Concomitant treatment with bisphosphonates or denosumab is permitted for treatment of osteoporosis or management of existing bone metastases if initiated at least 4 weeks before administration of the first dose of MLN0128.
3. Exclusion criterion 3 was removed as of Protocol Amendment 6.
4. Initiation of treatment with hematopoietic growth factors, transfusions of blood and blood products, or systemic corticosteroids (either IV or oral steroids, excluding inhalers) within 1 week before administration of the first dose of MLN0128 (patients already receiving erythropoietin on a chronic basis for  $\geq 4$  weeks are eligible).
5. Previous treatment with dual PI3K/mTOR inhibitors or TORC1/2 inhibitors.
6. Manifestations of malabsorption due to prior gastrointestinal (GI) surgery, GI disease, or for an unknown reason that may alter the absorption of MLN0128.
7. Poorly controlled diabetes mellitus defined as glycosylated hemoglobin (HbA1c)  $> 7\%$ ; patients with a history of transient glucose intolerance due to corticosteroid administration may be enrolled in this study if all other inclusion/exclusion criteria are met.
8. Other clinically significant co-morbidities, such as uncontrolled pulmonary disease, active central nervous system disease, active infection, or any other condition that could compromise participation of the patient in the study.
9. Known human immunodeficiency virus infection.

**MLN0128****Clinical Study Protocol C31001 Amendment 6, EudraCT: 2014-001921-34**

10. History of any of the following within the last 6 months before administration of the first dose of MLN0128:

- Ischemic myocardial event, including angina requiring therapy and artery revascularization procedures.
- Ischemic cerebrovascular event, including transient ischemic attack and artery revascularization procedures.
- Requirement for inotropic support (excluding digoxin) or serious (uncontrolled) cardiac arrhythmia (including atrial flutter/fibrillation, ventricular fibrillation, or ventricular tachycardia).
- Placement of a pacemaker for control of rhythm.
- New York Heart Association Class III or IV heart failure (see Section 14.2).
- Pulmonary embolism.

11. Significant active cardiovascular or pulmonary disease before administration of the first dose of MLN0128, including:

- Uncontrolled hypertension (ie, systolic blood pressure >180 mm Hg; diastolic blood pressure >95 mm Hg).
- Pulmonary hypertension.
- Uncontrolled asthma or oxygen saturation <90% by arterial blood gas analysis or pulse oximetry on room air.
- Significant valvular disease; severe regurgitation or stenosis by imaging independent of symptom control with medical intervention; or history of valve replacement.
- Medically significant (symptomatic) bradycardia.
- History of arrhythmia requiring an implantable cardiac defibrillator.

## **MLN0128**

### **Clinical Study Protocol C31001 Amendment 6, EudraCT: 2014-001921-34**

- Baseline prolongation of the rate-corrected QT interval (QTc; eg, repeated demonstration of QTc interval >480 msec, or history of congenital long QT syndrome, or torsades de pointes).

12. Diagnosed or treated for another malignancy within 2 years before administration of the first dose of MLN0128 or previously diagnosed with another malignancy and have any evidence of residual disease. Patients with nonmelanoma skin cancer or carcinoma in situ of any type are not excluded if they have undergone complete resection.

#### **5.2.2 Phase 1b Only**

In addition to the previously mentioned exclusion criteria, patients meeting the following exclusion criterion are not to be enrolled in the phase 1b portion of the study:

13. More than 3 prior chemotherapy regimens for locally advanced or metastatic disease.

#### **5.2.3 Phase 2 Only**

In addition to the previously mentioned exclusion criteria, patients meeting the following exclusion criterion are not to be enrolled in the phase 2 portion of the study:

14. More than 1 prior chemotherapy regimen for locally advanced or metastatic disease.

## **6. STUDY DRUG**

### **6.1 Study Drug Administration**

All protocol-specific criteria for administration of MLN0128 must be met and documented before drug administration. Study drug will be administered only to eligible patients under the supervision of the investigator or identified subinvestigator(s).

For all patients, MLN0128 will be administered QD at approximately the same time each day. It is recommended that each dose of MLN0128 be given orally with 8 ounces (240 mL) of water.

- *For patients receiving MLN0128 capsules with unmilled API:* MLN0128 will be administered with a light meal.

## **MLN0128**

### **Clinical Study Protocol C31001 Amendment 6, EudraCT: 2014-001921-34**

- *For patients receiving MLN0128 capsules with milled API:* MLN0128 will be administered on an empty stomach. The patients should be instructed to refrain from eating and drinking (except for water and prescribed medications) for 2 hours before and 1 hour after each dose.

If severe emesis or mucositis prevents the patient from taking an MLN0128 dose, that dose will be skipped. If emesis occurs after study medication ingestion and whole capsule(s) are visible in the vomitus, replacement capsule(s) should be taken; otherwise the dose will not be readministered, and patients should simply adhere to the dosing schedule and resume dosing at the next scheduled time with the prescribed dosage. Patients should record the time of the emesis in their dosing diary (see the Study Manual). Under no circumstance should a patient repeat a dose or double-up doses.

Exemestane and fulvestrant will be administered per their current USPIs or SmPCs, and according to the dose regimen administered before study entry.

#### **For patients assigned to receive MLN0128 in combination with exemestane:**

- MLN0128 should be administered first on an empty stomach (ie, nothing to eat or drink for 2 hours before and 1 hour after MLN0128 dosing).
- Patients should have a meal before taking their exemestane dose, which may be taken between 1 and 6 hours after MLN0128 dosing.

#### **6.2 Definitions of DLT for the Phase 1b Portion of the Study**

DLTs are defined according to the AE profile observed during the first 28 days of study drug administration in phase 1b of the study and as described below. All AEs should be considered possibly related to the study drug unless such relationship can be definitively excluded. In Part 2 of the phase 1b portion of the study:

- If  $\geq 2$  DLTs occur in the treatment group receiving 4 mg of MLN0128, the subsequent phase 2 portion of the study will be initiated at 3 mg of MLN0128 QD in combination with exemestane or fulvestrant.
- If  $\leq 1$  DLT occurs in the treatment group (either at 4 mg or 2 mg QD), the subsequent phase 2 portion of the study will be initiated at the same dose (either 2 mg or 4 mg of MLN0128 QD) in combination with exemestane or fulvestrant.

**MLN0128****Clinical Study Protocol C31001 Amendment 6, EudraCT: 2014-001921-34**

- If  $\geq 2$  DLTs occur in the treatment group receiving 2 mg of MLN0128 in combination with either exemestane and/or fulvestrant, the study will be stopped.

Toxicity will be evaluated according to the NCI CTCAE, version 4.03, effective 14 June 2010. These criteria are provided in the Study Manual. A DLT will be defined as any of the following events that are considered by the investigator to be at least possibly related to treatment with MLN0128 in combination with either exemestane or fulvestrant:

- Grade 3 or higher nonhematologic toxicity, despite adequate treatment, except for the following:
  - Grade 3 hyperglycemia lasting  $\leq 14$  days (all patients should receive optimal antihyperglycemic treatment, including insulin).
  - Grade 3 rash lasting  $\leq 3$  days (all patients should receive topical steroid treatment, oral antihistamines, and oral steroids, if necessary).
- Grade 4 neutropenia lasting  $>7$  days in the absence of growth factor support.
- Grade 4 neutropenia of any duration accompanied by fever  $\geq 38.5^{\circ}\text{C}$  and/or systemic infection.
- Any other  $\geq$ Grade 4 hematologic toxicity.
- Inability to administer at least 75% of planned doses of MLN0128 within Cycle 1 due to study drug-related toxicity.
- Any clinically significant occurrence that the investigator and sponsor agree would place patients at an undue safety risk.

Patients who experience an AE that meets the definition of a DLT during or after completing Cycle 1 should have their study drug treatment interrupted. If the event resolves to Grade 1 or baseline values within 2 weeks of interrupting planned therapy, and in the opinion of the investigator and the sponsor's project clinician the benefits of continuing treatment outweigh the risks posed by the toxicity, patients may continue study treatment with MLN0128 at a 25% to 50% dose reduction (ie, dose reduced from 4 mg to 3 mg [25%]; from 3 mg to 2 mg [33%]; or from 2 mg to 1 mg [50%] QD) with approval of the sponsor's project clinician. Alternatively, if dose modification is required for patients receiving 2 mg QD, then the dosing frequency may also be decreased to 5 days per week (28% reduction) instead of

## **MLN0128**

### **Clinical Study Protocol C31001 Amendment 6, EudraCT: 2014-001921-34**

decreasing the daily dose administered. If study drug dosing is delayed for more than 14 consecutive days for MLN0128-related toxicity, despite supportive treatment per standard clinical practice, or more than 2 dose reductions of MLN0128 are required, the patient will be discontinued from the study.

### **6.3 Dose-Modification Guidelines for the Phase 2 Portion of the Study**

#### **6.3.1 Dose Modification or Treatment Delay for MLN0128-Related Toxicity**

Based on the outcome of a safety and tolerability analysis performed in the phase 1b portion of the study, MLN0128 4 mg QD in combination with either exemestane or fulvestrant was determined as the phase 2 starting dose. Another safety and tolerability assessment will be performed during the phase 2 portion of the study where the first 6 patients treated with MLN0128 4 mg QD in combination with exemestane or fulvestrant who have completed 2 cycles of treatment with MLN0128 will be evaluated for TEAEs. Enrollment of patients into the study will continue during this safety and tolerability assessment.

In addition, during the phase 2 portion of the study, both tolerability and need for dose reductions and/or modifications will continue to be monitored for all patients in all cycles. If, based on this assessment, the 4 mg QD starting dose identified in Part 2 of the phase 1 portion is deemed unfavorable, in conjunction with agreement of the study investigators and the medical monitor, the starting dose may be adjusted to 2 or 3 mg QD for all newly enrolled patients to improve long-term tolerability. Patients who were enrolled at 3 or 4 mg QD in Part 2 of the phase 1 portion and the phase 2 portion will be maintained at this dose unless dose modifications are required due to individual tolerability. A starting dose reduction, if required, will be documented to all study sites by formal written communication.

MLN0128 administration should be withheld for MLN0128-related toxicities that are  $\geq$ Grade 3 despite supportive treatment per standard clinical practice. If the event resolves to Grade 1 or baseline values within 2 weeks of interrupting treatment, the patient may resume study treatment at a 25% to 50% dose reduction (ie, 2 mg QD). Alternatively, if dose modification is required for patients receiving 2 mg QD, then the dosing frequency should be decreased to 5 days per week instead of decreasing the daily dose administered. If MLN0128 dosing is delayed for more than 14 consecutive days for MLN0128-related toxicity despite supportive treatment per standard clinical practice, or more than 2 dose reductions of MLN0128 are required in a patient, stop MLN0128 therapy, discontinue the patient from the study, and complete the EOT visit within 30 to 40 days after the last dose of

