**MLN0128****Clinical Study Protocol C31001 Amendment 6, EudraCT: 2014-001921-34**

- No evidence of disease progression for  $\geq 3$  months or hemorrhage after treatment.
  - Off-treatment with dexamethasone for 4 weeks before administration of the first dose of MLN0128.
  - No ongoing requirement for dexamethasone or antiepileptic drugs.
5. Eastern Cooperative Oncology Group (ECOG) performance status 0 to 2 (refer to Section 14.1).
  6. Clinical laboratory values as specified below within 4 weeks before the first dose of MLN0128:
    - Bone marrow reserve consistent with absolute neutrophil count (ANC)  $\geq 1.5 \times 10^9/L$ ; platelet count  $\geq 100 \times 10^9/L$ ; hemoglobin  $\geq 9$  g/dL.
    - Total bilirubin  $\leq 1.5$  times the upper limit of the normal range (ULN), aspartate aminotransferase (AST) and alanine aminotransferase (ALT)  $\leq 2.5 \times \text{ULN}$  ( $\leq 5 \times \text{ULN}$  if liver metastases are present).
    - Creatinine clearance  $\geq 50$  mL/min based either on Cockcroft-Gault estimate (refer to Section 14.3) or based on a 12- or 24-hour urine collection.
    - Fasting serum glucose  $\leq 130$  mg/dL and fasting triglycerides  $\leq 300$  mg/dL.
  7. Left ventricular ejection fraction (LVEF) within 5 absolute percentage points of institutional standard of normal as measured by echocardiogram (ECHO) or multiple gated acquisition (MUGA) scan within 4 weeks before the first dose of MLN0128 (ie, if the institutional standard of normal is 50%, LVEF may be as low as 45% to be eligible for the study).
  8. Able to provide paraffin blocks or a minimum of 10 unstained slides of available archival tumor tissues (paraffin blocks are preferred). If archival tumor tissue is not available, a tumor biopsy may be performed before the patient begins treatment with MLN0128. If fewer than 10 slides are available or the tumor content/area requirements are not met, study eligibility will be determined upon discussion with the sponsor.

9. Ability to swallow oral medications, willingness to perform mucositis prophylaxis, and suitable venous access for the study-required blood sampling.
10. Voluntary written consent must be given before the performance of any study-related procedure not part of standard medical care, with the understanding that consent may be withdrawn by the patient at any time without prejudice to future medical care.

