**Table 6-1 Management of Hyperglycemia**

Grade	Description	Treatment	MLN0128 Dose Modification
1	FBG>ULN–160 mg/dL	Continue close monitoring of blood glucose. Initiate oral hypoglycemic agent.	None
2	FBG>160–250 mg/dL	Initiate oral hypoglycemic agent and/or insulin if not well controlled on oral agent.	None
$\geq 3$	FBG>250 mg/dL	Initiate oral hypoglycemic agent and/or insulin.	Hold drug until $\leq$ Grade 2. Resume MLN0128 based on timing of recovery: 
 
• <math>\leq 1</math> week: resume at same dose and schedule.
 
• <math>>1</math> but <math>\leq 2</math> weeks: reduce dose. (a)
 
• 2 weeks: stop MLN0128 and discontinue patient from the study.
 

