**Prevention/Prophylaxis**

- Follow fasting serum glucose levels during clinic visits.
- Monitor home glucometer test results.
- Check HbA1c levels every 3 months during therapy.
- Recommend lifestyle modifications, as appropriate (balanced diet, limited alcohol consumption, increased physical activity).
- Most episodes of Grade 1 and 2 hyperglycemia respond quickly to oral metformin. Early initiation of therapy is recommended to prevent higher-grade hyperglycemia.
- FBG levels  $\geq 150$  mg/dL by glucometer should be followed by closer monitoring of serum glucose and possible intervention.

QD $\times$ 5D=once daily for 5 days each week.

(a) Phase 1b Part 1 cohorts: for patients receiving a starting dose of 5 mg, reduce by 20% (to 4 mg). If dose modification is required for patients receiving  $\leq 4$  mg QD, then the frequency of dosing should be decreased to QD $\times$ 5D, rather than decreasing the daily dose administered. For all other patients: the initial dose reduction should be from 4 mg to 3 mg, with further reduction to 2 mg if necessary.

If any fasting serum glucose reading performed at the site indicates hyperglycemia ( $>$ ULN or  $\geq 110$  mg/dL), the study staff should first confirm that the patient was fasting at the time

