**Table 6-4 Management of Rash**

Grade	Description	Treatment	MLN0128 Dose Modification
≤2	Macules/papules covering ≤30% body surface area with or without symptoms	Consider treatment with topical steroid cream/ointment and/or oral antihistamines.	None
≥3	Macules/papules covering >30% body surface area with or without symptoms	Consider treatment with topical steroid cream/ointment, oral antihistamines, and/or pulsed steroids.	Hold until ≤Grade 2; resume MLN0128 based on timing of recovery: ≤2 weeks: reduce dose. (a) >2 weeks: stop MLN0128 and discontinue patient from the study.

QD×5D=once daily for 5 days each week.

(a) Phase 1b Part 1 cohorts: for patients receiving a starting dose of 5 mg, reduce by 20% (to 4 mg). If dose modification is required for patients receiving ≤4 mg QD, then the frequency of dosing should be decreased to QD×5D, rather than decreasing the daily dose administered. For all other patients: the initial dose reduction should be from 4 mg to 3 mg, with further reduction to 2 mg if necessary.

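### For phase 2 toxicity of Grade 3 or higher despite supportive treatment, Protocol Section 6.3.1 and the Section 6.7 tables conflict on restart dose and recovery grade, and nothing says which governs

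*Protocol*

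**What the plan says.** Protocol Section 6.3.1 gives one general rule for phase 2. MLN0128 is withheld for related toxicity of Grade 3 or higher that persists "despite supportive treatment per standard clinical practice. If the event resolves to Grade 1 or baseline values within 2 weeks of interrupting treatment", and on that recovery "the patient may resume study treatment at a 25% to 50% dose reduction (ie, 2 mg QD"). If dosing is delayed for more than 14 consecutive days for related toxicity, or more than two dose reductions are needed, treatment stops and the patient leaves the study.

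The tables in Section 6.7 set event-specific rules. Footnote (a), under Tables 6-1 to 6-4 and 6-6, sets phase 1b Part 1 apart and then states: "For all other patients: the initial dose reduction should be from 4 mg to 3 mg, with further reduction to 2 mg if necessary". That covers phase 2.

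- **Hyperglycemia (Table 6-1), Grade 3 or higher:** "Hold drug until $\leq$ Grade 2. Resume MLN0128 based on timing of recovery". If recovery takes a week or less, the instruction is to "resume at same dose and schedule".
- **Rash (Table 6-4), Grade 3 or higher:** "Hold until ≤Grade 2; resume MLN0128 based on timing of recovery", with a reduced dose if recovery comes within 2 weeks.
- **Nausea and vomiting (Table 6-5), Grade 3 or higher:** hold to Grade 1 or lower, then restart with the dose unchanged.

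Section 4.1.2 places the phase 2 dose-modification guidelines in Section 6.3. Section 6.7.2 presents Table 6-2 as guidance on MLN0128 dose modification. Section 6.3.1 requires contact with the sponsor's project clinician before any dose modification.

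**The concern.** Both sets of rules apply to the same phase 2 patients, and they differ on when MLN0128 may restart and at what dose. For some events, one passage restarts treatment and the other ends it for good. Sites that follow different passages would treat like patients differently.

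This is first a matter of patient safety and consistent conduct. It also reaches the analysis: SAP Section 7.7 tabulates dose reductions, holds, permanent discontinuations and relative dose intensity, and all of these would carry the inconsistency.

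**Working it through.** **Restart dose from the 4 mg phase 2 starting dose**

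Reduction = 1 − (new dose / old dose).

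- 4 to 3 mg: 1 − 3/4 = 25%
- 4 to 2 mg: 1 − 2/4 = 50%
- 4 to 4 mg: 1 − 4/4 = 0%
- 3 to 2 mg: 1 − 2/3 = 33%

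A 25% to 50% reduction from 4 mg therefore means 3 mg down to 2 mg. The parenthetical in Section 6.3.1 names only the 50% end, so it does not reproduce its own range. It would fit a patient who started at 3 mg, which Section 6.3.1 allows for newly enrolled patients if the starting dose is lowered. Footnote (a)'s first step (25%) is inside the range but contradicts the parenthetical. A same-dose restart (0%) is outside both.

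Weekly dose, in mg:

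- Section 6.3.1 read literally: 4×7 = 28, then 2×7 = 14, then 2×5 = 10 on the 5-day schedule
- Footnote (a): 4×7 = 28, then 3×7 = 21, then 2×7 = 14

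After one reduction the patient takes 14 or 21 mg a week, depending on the section followed.

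**The six tables against Section 6.3.1 (Grade 1 or baseline; 25% to 50% reduction)**

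| Table (Grade 3 event) | Recovery needed | Restart dose from 4 mg | Differs from 6.3.1 on |
|---|---|---|---|
| 6-1 Hyperglycemia | Grade 2 or lower | 4 mg if recovered in 1 week or less; otherwise 3 mg | grade; dose |
| 6-2 Hyperlipidemia | Grade 1 or lower | 3 mg | parenthetical only |
| 6-3 Oral mucositis | Grade 1 or lower | 3 mg | parenthetical only |
| 6-4 Rash | Grade 2 or lower | 3 mg | grade; parenthetical |
| 6-5 Nausea/vomiting | Grade 1 or lower | 4 mg | dose |
| 6-6 Pneumonitis | Grade 1 or lower | 3 mg (to be considered) | parenthetical only |

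**Does the baseline alternative close the recovery gap?**

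Not for glucose. Inclusion criterion 6 (Section 5.1.1) requires "Fasting serum glucose $\leq 130$ mg/dL" at screening. Table 6-1 defines Grade 2 as "FBG>160–250 mg/dL". The cap lies 160 − 130 = 30 mg/dL below the Grade 2 floor, so return to baseline cannot mean Grade 2. This assumes that glucose has not risen above 160 mg/dL between screening and the first dose. The disputed band is 250 − 160 = 90 mg/dL wide.

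**Two patients followed through both texts**

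- *Hyperglycemia:* Grade 3 despite treatment, down to 200 mg/dL on day 5 and steady there. Table 6-1 counts this as recovery within a week and resumes the same dose. Under Section 6.3.1 the event has not recovered; the hold continues and treatment stops after 14 days.
- *Rash:* Grade 3 despite treatment, Grade 2 by day 10 and steady there, with no Grade 2 rash at baseline. Table 6-4 restarts at a reduced dose. Section 6.3.1 keeps the hold and stops treatment after 14 days.

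**Order of precedence**

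The pointer in Section 4.1.2 favors Section 6.3. The introduction to Table 6-2 gives that table the same function. The contact requirement adds consultation but no rule for choosing. None of the three ranks the texts.

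**Two lesser points**

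- Read literally, the 14-day limit in Section 6.3.1 has no grade restriction, while Table 6-6 allows 4 weeks (28 days) for recovery from Grade 2 pneumonitis. If the limit belongs only with the Grade 3 hold rule, there is no conflict.
- Section 6.3.1 does not say whether its 5-day schedule counts toward the limit of two reductions. On the footnote (a) steps, 4 to 3 to 2 mg already uses both.

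**The case against.** The strongest objection concerns the trigger. Section 6.3.1 applies to toxicity that persists despite supportive treatment. The Grade 3 rows of Tables 6-1 and 6-5 tell the site to start or intensify such treatment. On that reading, quick recovery allows the same dose, refractory toxicity requires a reduction, and the texts fit together. This narrows the overlap, and events not yet fully treated are not in conflict. It does not remove the overlap: the rows cover every event of Grade 3 or higher, with no exception for refractory ones.

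Second, the 2 mg against 3 mg difference may be one loose parenthetical. Section 6.2 uses the same percentage range for phase 1b and spells it out as 4 to 3, 3 to 2 and 2 to 1 mg. This stands in part: if the range governs, 3 mg complies. It does not help with the same-dose restarts or the recovery grades.

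Third, a specific table may be read as overriding a general rule, and the permissive verb in Section 6.3.1 does not expressly bar restart at Grade 2. That is an ordinary reading, but the protocol does not state it and Section 4.1.2 points the other way. Discretion over restarting does not reconcile two recovery thresholds when a mandatory stop follows.

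Fourth, one sponsor role is contacted before every dose modification. That reduces variation between sites, but that role has no written rule to apply either.

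Finally, the pneumonitis and 5-day points are peripheral. That is accepted: the first is conditional and the second is missing detail. No effect on CBR-16 has been shown.

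**Conclusion.** The concern holds, limited to phase 2 MLN0128-related events of Grade 3 or higher despite supportive treatment. Confidence is high.

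- **Recovery grade:** two of six tables (hyperglycemia and rash) conflict with Section 6.3.1. Followed as written, the texts give restart or permanent stop for the same patient.
- **Same-dose restart:** Table 6-5, and Table 6-1 with recovery in a week or less, give 4 mg (100%) against 2 to 3 mg (50% to 75%). This rests on the table rows including refractory events, which they do not exclude.
- **First reduction:** 2 mg (50%) against 3 mg (75%), only if the parenthetical is taken at its word.
- **Hold limit:** 14 against 28 days for Grade 2 pneumonitis is minor and depends on the reading.

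The documents do not allow the number of affected patients to be computed. The protocol should be corrected because the passages contradict each other on restarting and stopping treatment. No view is taken here on which dose or recovery rule is right.

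**What to change.** Reconcile the parenthetical, recovery threshold and hold limit in Section 6.3.1 with the Section 6.7 tables. Add one sentence stating whether Section 6.3.1 or the event table governs where they differ, and one stating whether the 5-day schedule counts toward the two-reduction limit. Investigator discretion over restarting can stay. The content of the reconciled rules is for the sponsor's clinicians.

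The change is wording only, with no new procedures, visits or SAP analyses. It needs a protocol amendment with written IRB/IEC approval (Section 10.8), rolled out to about 40 centers in three countries (Section 4.2).

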## **MLN0128**

### **Clinical Study Protocol C31001 Amendment 6, EudraCT: 2014-001921-34**

Patients in the Everolimus-Resistant Cohort and in the Everolimus-Sensitive Cohort who are not response evaluable (refer to Section 8.1.3) will need to be replaced.

Note that some patients may discontinue MLN0128 for reasons other than progressive disease. These patients will remain in the study for posttreatment assessments as outlined in the [Schedule of Events](#) and in Section 7.10.

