#### **7.8 Withdrawal of Patients From Study**

A patient may be withdrawn from the study for any of the following reasons:

- Lost to follow-up.
- Study terminated by sponsor.
- Withdrawal by patient.
- Other.

The consequence of study withdrawal is that no new information will be collected from the withdrawn patient and added to the existing data or any database.

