#### **7.9 Study Compliance**

Study drug will be administered or dispensed only to eligible patients under the supervision of the investigator or identified subinvestigator(s). The appropriate study personnel will maintain records of study drug receipt and dispensing.

Patients will receive a sufficient quantity of MLN0128 for each treatment cycle and a diary in which to record their dosing. Patients should continue taking the same dose of either exemestane or fulvestrant as previously administered. The study center staff will check the patient's diary versus the patient's supply of remaining MLN0128 and either exemestane or fulvestrant at each study visit to ensure proper compliance with dosing. Patients who are not compliant with the dosing schedule may be withdrawn from the study.

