#### **7.10 Posttreatment Follow-up Assessments (PFS and OS)**

After EOT, patients will be followed for PFS and OS. Survivor information may be collected by methods that include, but are not limited to, telephone, email, mail, or retrieved from online or other databases (eg, Social Security indexes). In addition, the start of another anticancer therapy will be collected. For those patients who discontinue MLN0128 for any

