The number and percentage of subjects experiencing treatment emergent AEs resulting in discontinuation of study drug (action on study drug=DISCONTINUED FROM STUDY) will be summarized by MedDRA system organ class, and preferred term.

A by-subject listing of treatment-emergent AEs resulting in discontinuation of study drug and treatment-emergent AEs resulting in dose modifications (held or reduced) will be generated.

A by-subject listing of the deaths will be presented. An on-study death is defined as a death that occurs between the first dose of study drug and within 30 days of the last dose of study drug.

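### Section 6 of the protocol takes toxicity stoppers off the study while Sections 4.3, 7.7 and 7.10 keep them in follow-up; read literally, Section 6 loses phase 2 PFS and OS data selectively

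*Protocol*

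**What the plan says.** **Text that ends study participation.** For phase 2, Protocol 6.3.1 deals with MLN0128-related toxicity that delays dosing for more than 14 consecutive days or needs more than two dose reductions. The site is told to "stop MLN0128 therapy, discontinue the patient from the study, and complete the EOT visit within 30 to 40 days after the last dose of" MLN0128. For the same situation in phase 1b, Section 6.2 states that "the patient will be discontinued from the study". Tables 6-1 (hyperglycemia) and 6-4 (rash) both contain the instruction "stop MLN0128 and discontinue patient from the study". Section 7.8 adds: "The consequence of study withdrawal is that no new information will be collected from the withdrawn patient".

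**Text that keeps the patient in.** Section 7.7 lists an adverse event among the reasons for stopping MLN0128. Of patients who stop for reasons other than progression it says "These patients will remain in the study for posttreatment assessments as outlined in the" Schedule of Events and Section 7.10. Section 7.10 states "After EOT, patients will be followed for PFS and OS", and Section 4.3 says the same after describing discontinuation for unacceptable toxicity. Schedule footnote b makes the EOT visit the point of entry to posttreatment follow-up. Footnote g asks for continued scans after any stop other than for radiographic progression.

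**SAP.** Section 7.11.1 selects adverse events that led to stopping study drug by the label "action on study drug=DISCONTINUED FROM STUDY". Section 7.3 summarises the reason for stopping drug and the end-of-study reason as two separate phase 2 items.

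**The concern.** A site facing prolonged toxicity will turn to Section 6, because that is where the dose rules are. If it does what Section 6 says and then applies Section 7.8, it makes no further scans or survival calls. A site that turns to Section 7.7 or 7.10 carries on with both. One patient could therefore be handled in two ways depending on the page consulted.

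The loss would be selective, because toxicity triggers it. PFS and OS are phase 2 secondary endpoints analysed by Kaplan-Meier. PFS is analysed in the Safety Population, so toxicity stoppers are included. Without progression they are censored at their last assessment of SD or better; for OS, patients are censored when last known alive. The SAP has no rule for study exit because of toxicity. If stoppers have a worse prognosis than the rest, this censoring is informative, and a study without a comparator has nothing to offset it.

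**Working it through.** The plan states no figure on this point, so the main check is a comparison of the texts.

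| Place | Drug | Study participation |
|---|---|---|
| 6.2 (phase 1b) | further dosing ends | ends |
| 6.3.1 (phase 2) | stop | ends; EOT visit required |
| Tables 6-1, 6-4 | stop | ends |
| Tables 6-2, 6-3, 6-6 | stop | not mentioned |
| 7.7, AE as reason | stop | continues |
| 4.3, 7.10, footnotes b and g | stop | continues after EOT |

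The difference is not just loose vocabulary. Section 7.5 ties completion of treatment to 7.7, and Section 7.6 ties completion of study to 7.8, so the protocol treats these as two events. Section 6.3.1 lists them as two acts in one sentence. Section 6.7 is also inconsistent within itself, since three of its tables stop only the drug.

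**Endpoints exposed.**
- Phase 1b: SAP 7.8 plans only efficacy listings, so Section 6.2 does not affect a PFS or OS estimate.
- CBR-16: response-evaluable status needs one dose and measurable disease, not a postbaseline scan. The interim analyses count patients who stop before the end of Cycle 4, so early stoppers stay in the denominator.
- PFS: SAP Table 7.a already censors at the last adequate assessment before new therapy. Later progression in such stoppers is excluded under either reading.
- OS: there is no such censoring, so this is the cleaner exposure.

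**Illustration of size.** Every input here is an assumption. Let λ = ln 2 / median, let a fraction f be due to stop at a time uniform on (a, b), and let the hazard be multiplied by h after the stop. For t > b:

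- Without the stop effect: S0(t) = exp(−λt). Kaplan-Meier estimates this if stoppers are censored when they stop.
- Stoppers: S1(t) = exp(−hλt) · M, with M = [e^((h−1)λb) − e^((h−1)λa)] / [(h−1)λ(b−a)].
- True survival: (1−f)S0 + f·S1. Overstatement: f(S0 − S1).

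*6-month PFS, stops at 0.5-3 months, median 3 or 5 months, f = 0.1-0.3.*
- Smallest (median 3, f = 0.1, h = 1.5): S0 = 0.250; S1 = 0.125 × 1.228 = 0.1535; true = 0.9 × 0.250 + 0.1 × 0.1535 = 0.240. Overstated by 1.0 point. Simulation with 400,000 patients: 0.240 against 0.250.
- Largest (median 5, f = 0.3, h = 2): S0 = 0.4353; S1 = 0.1895 × 1.281 = 0.2427; true = 0.7 × 0.4353 + 0.3 × 0.2427 = 0.3775. Overstated by 5.8 points. Simulation: 0.377 against 0.434.
- The median is overstated by about 0.05-0.7 months, and the PFS outcome of about 7-24% of patients is lost.
- At h = 1 the curves coincide: no bias, only lost events.

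*12-month OS, median 24 months, stops at 0.5-4 months, censored one month after stopping, 100,000 simulated patients.*

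| f | h | true | Kaplan-Meier | overstated (points) |
|---|---|---|---|---|
| 0.1 | 1.5 | 0.699 | 0.707 | 0.8 |
| 0.1 | 2 | 0.693 | 0.708 | 1.5 |
| 0.2 | 1.5 | 0.689 | 0.706 | 1.7 |
| 0.2 | 2 | 0.672 | 0.702 | 3.0 |
| 0.3 | 1.5 | 0.678 | 0.702 | 2.4 |
| 0.3 | 2 | 0.656 | 0.702 | 4.6 |

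The formula gives a true value of 0.7 × 0.7071 + 0.3 × 0.5338 = 0.655 for the last row, in agreement.

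**The case against.** The strongest reply is that the protocol, read as a whole, already handles these patients. Section 4.3 deals with toxicity and then follows patients for PFS and OS. The EOT visit that 6.3.1 requires is, by footnote b, the entry to follow-up. Section 7.8 does not list toxicity; only its category for other reasons could cover it. So linking 6.3.1 to the end of data collection is an inference. This stands: it makes the loss conditional on how a site reads the text. It does not remove the conflict, because Section 6 still says the patient leaves the study.

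A reader might go further in four ways that the documents do not support:

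- **That no data are collected after a toxicity stop.** The EOT visit is still required and related SAEs remain reportable. What is at risk is post-EOT scans and survival data, at sites that take Section 6 literally.
- **That the data capture merges stopping drug with leaving the study.** SAP 7.3 reports the two reasons separately. The label in 7.11.1 is ambiguous but does not show that follow-up ends.
- **That the curves are known to be flattered.** No stopping rate, post-stop hazard or expected PFS or OS is given.
- **That Section 7.9 is part of the contradiction.** Its sentence, "Patients who are not compliant with the dosing schedule may be withdrawn from the study", is permissive and concerns compliance, not toxicity.

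It is also fair to say that efficacy analysis is descriptive and no decision rule uses PFS or OS. One run with scans on the protocol calendar (median PFS 4 months, 20% stopping, hazard ratio 2) gave 37.0% against 35.2% at 6 months, a shift of 1.8 points. The 95% half-width for 37% is 1.96 × √(0.37 × 0.63 / n), or 13.7 points at n = 48 and 12.6 at n = 56. That keeps the point modest.

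**Conclusion.** This is a real internal inconsistency of low to moderate severity. Sections 6.2 and 6.3.1 and Tables 6-1 and 6-4 cannot be followed together with Sections 4.3, 7.7 and 7.10. The consequence is conditional: where Section 6 is applied literally, phase 2 PFS and OS lose outcomes selectively in toxicity stoppers, OS more cleanly than PFS.

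The text conflict is certain; the size of any bias is not. The ranges of about 1-6 points for 6-month PFS and 1-4.5 points for 12-month OS assume 10-30% stopping, a post-stop hazard ratio of 1.5-2, the medians stated above and every stopper lost. They would be smaller if only some sites stopped follow-up. The PFS figures also ignore censoring at new therapy, which removes part of the difference. The primary endpoint and the interim rules do not rest on this point.

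**What to change.** - In Protocol 6.2, 6.3.1 and Tables 6-1 and 6-4, reconcile the wording with 4.3, 7.7 and 7.10. Make stopping MLN0128 and leaving the study separate events, and say that patients who stop for toxicity enter the posttreatment follow-up already in the Schedule of Events.
- In SAP 7.11.1, state that the label means discontinuation of study drug, distinct from the end-of-study reason in SAP 7.3.

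The criteria for stopping MLN0128 are not touched, and Section 7.9 needs no change. The cost is a few wording edits in an amendment and one SAP line. No visits or scans are added, because the follow-up is already scheduled.
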